8.1.9.2 Time to the First Hospitalization due to SAE

Analyses of adverse events will include only "treatment-emergent" events. "Treatment emergent adverse events" are defined as any adverse events that first occur on or after the date of first dose of study drug and with an onset date no more than 30 days after the last dose date of study drug. Thus, the data included in this section is from first dosing of study drug to last dose date of study drug + 30 days.

Time to 1st Hospitalization After Achieving CR

Time to the 1st hospitalization after achieving CR will be defined as number of days from achieving CR to the first hospitalization. If a subject did not have any hospitalization, the subject's data will be censored at 30 days after the last dose date of study drug or death of any cause, whichever occurs earlier. Subjects who achieve CR will be included in the analysis.

Time to 1st Hospitalization After Achieving CRh

Time to the 1st hospitalization after achieving CRh will be defined as number of days from achieving CRh to the first hospitalization. If a subject did not have any hospitalization, the subject's data will be censored at 30 days after the last dose date of study drug or death of any cause, whichever occurs earlier. Subjects who achieve CRh will be included in the analysis.

Time to the 1st Hospitalization After Achieving CR/CRh

Time to the 1st hospitalization from achieving CR/CRh will be defined as number of days from achieving CR/CRh to the 1st hospitalization. If a subject did not have any hospitalization, the subject's data will be censored at 30 days after the last dose date of study drug or death of any cause, whichever occurs earlier. Subjects who achieve CR/CRh will be included in the analysis.

Time to the 1st Hospitalization Before Achieving CR

Time to the 1st hospitalization before achieving CR will be defined as number of days from the 1st date of study drug to the 1st hospitalization before achieving CR. If a subject did not have any hospitalization event, the subject's data will be censored at date that CR is first achieved. Subjects who achieve CR will be included in the analysis.

Time to the 1st Hospitalization Before Achieving CRh

Time to the 1st hospitalization before achieving CRh will be defined as number of days from the 1st date of study drug to the 1st hospitalization before achieving CRh. If a subject did not have any hospitalization event, the subject's data will be censored at date that CRh is first achieved. Subjects who achieve CRh will be included in the analysis.

Time to the 1st Hospitalization Before Achieving CR/CRh

Time to the 1st hospitalization before achieving CR/CRh will be defined as number of days from the 1st date of study drug to the 1st hospitalization before achieving CR/CRh. If a subject did not have any hospitalization event, the subject's data will be censored at date that CR/CRh is first achieved. Subjects who achieve CR/CRh will be included in the analysis.

Time to the 1st Hospitalization from 60 Days After the First Dose of Study Drug

Time to the 1st hospitalization from 60 days after the first dose of study drug will be defined as number of days from 60 days after first dose date of study drug to the

1st hospitalization. If a subject did not have any hospitalizations, the subject's data will be censored at 30 days after the last dose date of study drug or death of any cause, whichever occurs earlier. This analysis will be performed for subjects who achieve CR, achieve CR/CRh, and don't achieve CR or CRh separately.

Time to the 1st Hospitalization After 1st Date of Study Drug

Time to the 1st hospitalization after 1st date of study drug will be defined as number of days from first dose date of study drug to the 1st hospitalization. If a subject did not have any hospitalizations, the subject's data will be censored at 30 days after the last dose date of study drug or death of any cause, whichever occurs earlier. This analysis will be performed for subjects who achieve CR, achieve CR/CRh, and don't achieve CR or CRh separately.

8.1.9.3 Time to First Event of Grade 3 or Above TEAE of Haemorrhages (Narrow SMQ)

Analyses of adverse events will include only "treatment-emergent" events. "Treatment emergent adverse events" are defined as any adverse events that first occur on or after the date of first dose of study drug and with an onset date no more than 30 days after the last dose date of study drug. Thus, the data included in this section is from first dosing of study drug to last dose date of study drug + 30 days.

Time to First Event of Grade 3 or Above TEAE of Haemorrhages (Narrow SMQ) from Achieving CR

Time to the first event of Grade 3 or above TEAE of Haemorrhages from achieving CR will be defined as number of days from achieving CR to the first event of Grade 3 or above TEAE of Haemorrhages. If a subject did not have any Grade 3 or above TEAE of Haemorrhages, the subject's data will be censored at 30 days after the last dose date of study drug or death of any cause, whichever occurs earlier. Subjects who achieve CR will be included in the analysis.

Time to First Event of Grade 3 or Above TEAE of Haemorrhages (Narrow SMQ) from Achieving CRh

Time to the first event of Grade 3 or above TEAE of Haemorrhages from achieving CRh will be defined as number of days from achieving CRh to the first event of Grade 3 or above TEAE of Haemorrhages. If a subject did not have any Grade 3 or above TEAE of Haemorrhages, the subject's data will be censored at 30 days after the last dose date of study drug or death of any cause, whichever occurs earlier. Subjects who achieve CRh will be included in the analysis.

Time to the First Event of Grade 3 or Above TEAE of Haemorrhages (Narrow SMQ) from Achieving CR/CRh

Time to the first event of Grade 3 or above TEAE of Haemorrhages from achieving CR/CRh will be defined as number of days from achieving CR/CRh to the first event of Grade 3 or above TEAE of Haemorrhages. If a subject did not have any Grade 3 or above TEAE of Haemorrhages, the subject's data will be censored at 30 days after the last dose date of study drug or death of any cause, whichever occurs earlier. Subjects who achieve CR/CRh will be included in the analysis.

Time to the First Event of Grade 3 or Above TEAE of Haemorrhages (Narrow SMQ) Before Achieving CR

Time to the 1st first event of Grade 3 or above TEAE of Haemorrhages (narrow SMQ) before achieving CR will be defined as number of days from the 1st date of study drug to the 1st Grade 3 or above haemorrhages event before achieving CR. If a subject did not have any Grade 3 or above TEAE of Haemorrhages (narrow SMQ), the subject's data will be censored at date that CR is first achieved. Subjects who achieve CR will be included in the analysis.

Time to the First Event of Grade 3 or Above TEAE of Haemorrhages (Narrow SMQ) Before Achieving CRh

Time to the 1st event of Grade 3 or above TEAE of Haemorrhages (narrow SMQ) before achieving CRh will be defined as number of days from the 1st date of study drug to the 1st Grade 3 or above haemorrhages event before achieving CRh. If a subject did not have any Grade 3 or above TEAE of Haemorrhages (narrow SMQ), the subject's data will be censored at date that CRh is first achieved. Subjects who achieve CRh will be included in the analysis.

Time to the First Event of Grade 3 or Above TEAE of Haemorrhages (Narrow SMQ) Before Achieving CR/CRh

Time to the 1st event of Grade 3 or above TEAE of Haemorrhages (narrow SMQ) before achieving CR/CRh will be defined as number of days from the 1st date of study drug to the 1st Grade 3 or above Haemorrhage event before achieving CR/CRh. If a subject did not have any Grade 3 or above TEAE of Haemorrhages (narrow SMQ), the subject's data will be censored at date that CR/CRh is first achieved. Subjects who achieve CR/CRh will be included in the analysis.

Time to the First Event of Grade 3 or Above TEAE of Haemorrhages (Narrow SMQ) from 60 Days After the First Dose of Study Drug

Time to the first event of Grade 3 or above TEAE of Haemorrhages (narrow SMQ) from 60 days after the first dose of study drug will be defined as number of days from 60 days after first dose date of study drug to the first event of Grade 3 or above TEAE of Haemorrhages (narrow SMQ). If a subject did not have any events of Grade 3 or above TEAE of Haemorrhages (narrow SMQ), the subject's data will be censored at 30 days after the last dose date of study drug or death of any cause, whichever occurs earlier. This analysis will be performed for subjects who achieve CR, achieve CR/CRh, and don't achieve CR or CRh separately.

Time to the First Event of Grade 3 or Above TEAE of Haemorrhages (Narrow SMQ) from the First Dose of Study Drug

Time to the first event of Grade 3 or above TEAE of Haemorrhages (narrow SMQ) from first dose of study drug will be defined as number of days from first dose date of study drug to the first event of Grade 3 or above TEAE of Haemorrhages (narrow SMQ). If a subject did not have any events of Grade 3 or above TEAE of Haemorrhages (narrow SMQ), the subject's data will be censored at 30 days after the last dose date of study drug or death of any cause, whichever occurs earlier. This analysis will be performed for subjects who achieve CR, achieve CR/CRh, and don't achieve CR or CRh separately.

Time to 1st serious Haemorrhages (narrow SMQ) will be performed using the same method if data is available.

8.1.9.4 Time to First Event of Grade 3 or Above TEAE of Infections/Infestations (SOC)

Time to First Event of Grade 3 or Above TEAE of Infections/Infestations (SOC) from Achieving CR

Time to the first event of Grade 3 or above TEAE of infections/infestations (SOC) from achieving CR will be defined as number of days from achieving CR to the first event of Grade 3 or above TEAE of infections/infestations (SOC). If a subject did not have any Grade 3 or above TEAE of infections/infestations (SOC), the subject's data will be censored at 30 days after the last dose date of study drug or death of any cause, whichever occurs earlier. Subjects who achieve CR will be included in the analysis.

Time to First Event of Grade 3 or Above TEAE of Infections/Infestations (SOC) from Achieving CRh

Time to the first event of Grade 3 or above TEAE of infections/infestations (SOC) from achieving CRh will be defined as number of days from achieving CRh to the first event of Grade 3 or above TEAE of infections/infestations (SOC). If a subject did not have any

Grade 3 or above TEAE of infections/infestations (SOC), the subject's data will be censored at 30 days after the last dose date of study drug or death of any cause, whichever occurs earlier. Subjects who achieve CRh will be included in the analysis.

Time to First Event of Grade 3 or Above TEAE of Infections/Infestations (SOC) from Achieving CR/CRh

Time to the first event of Grade 3 or above TEAE of infections/infestations (SOC) from achieving CR/CRh will be defined as number of days from achieving CR/CRh to the first event of Grade 3 or above TEAE of infections/infestations (SOC). If a subject did not have any Grade 3 or above TEAE of infections/infestations (SOC), the subject's data will be censored at 30 days after the last dose date of study drug or death of any cause, whichever occurs earlier. Subjects who achieve CR/CRh will be included in the analysis.

Time to the First Event of Grade 3 or Above TEAE of Infections/Infestations (SOC) Before Achieving CR

Time to the 1st first event of Grade 3 or above TEAE of infections/infestations (SOC) before achieving CR will be defined as number of days from the 1st date of study drug to the 1st event of Grade 3 or above TEAE of infections/infestations (SOC) before achieving CR. If a subject did not have any Grade 3 or above TEAE of infections/infestations (SOC), the subject's data will be censored at date that CR is first achieved. Subjects who achieve CR will be included in the analysis.

Time to the First Event of Grade 3 or Above TEAE of Infections/Infestations (SOC) Before Achieving CRh

Time to the 1st event of Grade 3 or above TEAE of infections/infestations (SOC) before achieving CR will be defined as number of days from the 1st date of study drug to the 1st event of Grade 3 or above TEAE of infections/infestations (SOC) before achieving CRh. If a subject did not have any Grade 3 or above TEAE of infections/infestations (SOC), the subject's data will be censored at date that CRh is first achieved. Subjects who achieve CRh will be included in the analysis.

Time to the First Event of Grade 3 or Above TEAE of Infections/Infestations (SOC) Before Achieving CR/CRh

Time to the 1st event of Grade 3 or above TEAE of infections/infestations (SOC) before achieving CR/CRh will be defined as number of days from the 1st date of study drug to the 1st event of Grade 3 or above TEAE of infections/infestations (SOC) before achieving CR/CRh. If a subject did not have any Grade 3 or above TEAE of infections/infestations (SOC), the subject's data will be censored at date that CR/CRh is first achieved. Subjects who achieve CR/CRh will be included in the analysis.

Time to First Event of Grade 3 or Above TEAE of Infections/Infestations (SOC) from 60 Days After the First Dose of Study Drug

Time to the first event of Grade 3 or above TEAE of infections/infestations (SOC) from 60 days after the first dose of study drug will be defined as number of days from 60 days after first dose date of study drug to the first event of Grade 3 or above TEAE of infections/infestations (SOC) during the treatment period. If a subject did not have any events of Grade 3 or above TEAE of infections/infestations (SOC), the subject's data will be censored at 30 days after the last dose date of study drug or death of any cause, whichever occurs earlier. This analysis will be performed for subjects who achieve CR, achieve CR/CRh, and don't achieve CR or CRh separately.

Time to First Event of Grade 3 or Above TEAE of Infections/Infestations (SOC) from the First Dose of Study Drug

Time to the first event of Grade 3 or above TEAE of infections/infestations (SOC) from first dose of study drug will be defined as number of days from first dose date of study drug to the first event of Grade 3 or above TEAE of infections/infestations (SOC). If a subject did not have any events of Grade 3 or above TEAE of infections/infestations (SOC), the subject's data will be censored at 30 days after the last dose date of study drug or death of any cause, whichever occurs earlier. This analysis will be performed for subjects who achieve CR, achieve CR/CRh, and don't achieve CR or CRh separately.

Time to 1st serious infections/infestations (SOC) will be performed using the same method if data is available.

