8.1.9 Time to the First Event

For each analysis set, the distribution of time to event for each parameter described in below sections will be estimated using Kaplan-Meier methodology. Median time to the first event for each parameter listed below with the corresponding 95% CI will be provided from Kaplan-Meier estimation. All data available in the extracted database will be used for the analyses described in Section [8.1.9](#).

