8.1.9.1 Transfusion

The transfusion data was designed to be collected during the treatment period and until the 30 day follow-up visit. Thus, the data included in this section is from the first dose date of study drug to the last dose of study drug + 30 days. Transfusion data will be summarized as RBC transfusion and platelet transfusion separately.

Time to 1st RBC/Platelet Transfusion After Achieving CR

Time to 1st RBC/platelet transfusion after achieving CR will be defined as number of days from achieving CR to the first RBC/platelet transfusion. If a subject did not have any RBC/platelet transfusion events, the subject's data will be censored at 30 days after the last dose date of study drug or death of any cause, whichever occurs earlier. Subjects who achieve CR will be included in the analysis.

Time to 1st RBC/Platelet Transfusion After Achieving CRh

Time to 1st RBC/platelet transfusion after achieving CRh will be defined as number of days from achieving CRh to the first RBC/platelet transfusion. If a subject did not have any RBC/platelet transfusion events, the subject's data will be censored at 30 days after the last dose date of study drug or death of any cause, whichever occurs earlier. Subjects who achieve CRh will be included in the analysis.

Time to 1st RBC/Platelet Transfusion After Achieving CR/CRh

Time to 1st RBC/platelet transfusion after achieving CR/CRh will be defined as number of days from achieving CR/CRh to the first RBC/platelet transfusion. If a subject did not have any RBC/platelet transfusion, the subject's data will be censored at 30 days after the last dose date of study drug or death of any cause, whichever occurs earlier. Subjects who achieve CR/CRh will be included in the analysis.

Time to the 1st RBC/Platelet Transfusion Before Achieving CR

Time to the 1st RBC/platelet transfusion before achieving CR will be defined as number of days from the 1st date of study drug to the 1st RBC/platelet transfusion before achieving CR. If a subject did not have any RBC/platelet transfusion before achieving CR, the subject's data will be censored at the date that CR is first achieved. Only subjects who achieve CR will be included in the analysis.

Time to the 1st RBC/Platelet Transfusion Before Achieving CRh

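### Twelve analyses of events before remission use Kaplan-Meier with remission as censoring, so their medians can misstate how many responders had an event; nine of the censoring rules are also incomplete

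*SAP*

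**What the plan says.** The opening paragraph of SAP Section 8.1.9 sets one method for everything below it: "For each analysis set, the distribution of time to event for each parameter described in below sections will be estimated using Kaplan-Meier methodology". The reported summary is also fixed there: "Median time to the first event for each parameter listed below with the corresponding 95% CI will be provided from Kaplan-Meier estimation".

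Sections 8.1.9.1 to 8.1.9.4 then define four event types (RBC/platelet transfusion, hospitalisation due to SAE, Grade 3 or higher haemorrhage, Grade 3 or higher infection). Each has a version before CR, before CRh and before CR/CRh, which makes 4 × 3 = 12 definitions. All twelve share three features:

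- The clock starts at first dose of study drug.
- Only subjects who reach the named remission enter. For transfusion: "Only subjects who achieve CR will be included in the analysis". For hospitalisation: "Subjects who achieve CR will be included in the analysis".
- The remission date is the censoring date.

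The censoring condition is worded in two ways. In 8.1.9.1 it applies to a subject who "did not have any RBC/platelet transfusion before achieving CR, the subject's data will be censored at the date that CR is first achieved". In 8.1.9.2 the condition stops earlier: "If a subject did not have any hospitalization event, the subject's data will be censored at date that CR is first achieved". Sections 8.1.9.3 and 8.1.9.4 follow the shorter form, so it covers 3 × 3 = 9 of the 12 definitions.

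No count or percentage of responders with an event before remission is planned for these windows, nor any cumulative incidence with remission as a competing event.

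**The concern.** Kaplan-Meier censoring is meant for subjects whose outcome is unknown after some date. Here the question is what happened between first dose and remission, and inclusion requires that remission was reached. Each subject's window has a known end, and whether an event fell inside it is a yes/no fact. Event-free subjects are nonetheless treated as if their outcome were still open, and the estimator projects later events onto them.

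The result describes event risk while still not in remission, as if remission had not come, in a group selected because it did come. A reader shown a median would naturally take it as the time by which half of the responders had been transfused, admitted, or had bled. It need not mean that.

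The shorter censoring condition adds a programming problem. A subject whose only hospitalisation came after CR has no event before CR, yet does not satisfy the condition for being censored. Read literally, the rule assigns that subject no date at all.

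**Working it through.** **No plan figure to reproduce.** These clauses state no number. As an input check on group size, SAP Table 7 gives a targeted CR rate of 21% (13%, 31%) in 82 subjects at 600 mg. Clopper-Pearson for 17/82 gives 20.7% (12.6%, 31.1%), so a CR-only analysis would hold about 17 people.

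**Remission times.** The protocol (5.3.3, Reporting of Results) assesses response at Cycle 2 Day 1, Cycle 4 Day 1 and every 3 cycles after that. With 28-day cycles this is about 28, 84 and 168 days after first dose.

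**Direction.** Kaplan-Meier passes the weight of each censored subject to those still at risk, so any later event carries extra weight. Hence 1 − KM ≥ events/N, with equality when no event follows a censoring at remission.

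**Illustration (assumed data).** Seventeen CR subjects, 5 with an event before CR: two before day 28, two between days 28 and 84, one at day 120. The other 12 reach CR event-free: 5 at day 28, 6 at day 84, 1 at day 168.

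- After two events: S = 15/17 = 0.882. Five are censored at day 28, leaving 10 at risk.
- After two more: S = 15/17 × 8/10 = 0.706. Six are censored at day 84, leaving 2.
- At day 120: S = 0.706 × 1/2 = 0.353.

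The SAP method gives a plateau of 1 − 0.353 = 65% and a median of day 120. The observed share is 5/17 = 29% (Clopper-Pearson 95% CI 10% to 56%), so fewer than half had an event.

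**Size under a constant hazard λ.** Let w be the shares of CR at days 28, 84 and 168. The true share is p = Σ w(1 − exp(−λt)); the Kaplan-Meier plateau is 1 − exp(−168λ). Setting p = 30%:

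| CR split (28/84/168) | λ per day | 1 − KM at day 168 |
|---|---|---|
| 70/20/10 | 0.00758 | 72% |
| 40/40/20 | 0.00493 | 56% |
| 20/50/30 | 0.00383 | 47% |

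**Size by event timing.** The documents give neither event rates nor times, so these are assumed ranges: true share 10% to 70%, the three splits above, and a continuous remission-time variant.

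| Timing of events | 1 − KM minus true share |
|---|---|
| All before the first response marrow | 0 points (ratio 1.00) |
| Hazard decaying, 14-day half-life | 1 to 8 points |
| Hazard four times higher in cycle 1 | 4 to 28 points |
| Constant hazard | 7 to 44 points (ratio 1.3 to 3.0) |

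**The median in a small group.** With n = 17 and a true share of 30%, in 1,000 simulated trials per setting, a Kaplan-Meier median was reported although fewer than half had an event in 39% to 61% of runs (constant hazard) and 22% to 29% (hazard four times higher in cycle 1).

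**The missing censoring date.** Suppose, in the illustration, 4 of the 12 event-free subjects were first hospitalised after CR and were dropped for want of a date. The share would become 5/13 = 38% instead of 5/17 = 29%. Only non-events can be lost this way, so dropping them biases the share upward.

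**The case against.** The SAP announces a time-to-event distribution and a median. It promises no proportion and no measure of burden. If remission time is independent of the event process, Kaplan-Meier correctly recovers the event-time curve while not in remission, which is a legitimate quantity. That stands, but it is not what the label suggests, and the SAP does not tell the reader how to take it.

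A reader might infer more: that the before-remission figures are greatly overstated, and that set beside the after-remission figures they exaggerate the benefit of remission. The documents do not support either step. The size turns on event timing that they do not give, and it can be nil. Nor does the SAP say that the before and after results will be contrasted to show benefit. With an equal constant rate on both sides and independent censoring, the two Kaplan-Meier curves agree: 1 − exp(−6 × rate) at 6 months is 45%, 83% and 97% for rates of 0.1, 0.3 and 0.6 per month, before and after alike. The crude share is no fairer for such a contrast, because it depends on the length of the window. This is why a rate per patient-month belongs beside it.

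On the nine rules, the defining sentence in each does limit the event to the period before remission, and the transfusion text shows the likely intent. The gap is one of wording, but it leaves the programmer to choose.

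The stakes are modest. SAP Section 9.0 plans no formal testing, and CR, CR + CRh, ORR, duration of response and OS are untouched.

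**Conclusion.** The point holds in a limited form. The twelve definitions apply Kaplan-Meier to windows that are complete for essentially every included subject. The small exception is a remission first documented more than 30 days after last dose, beyond the event collection window. Taken as the share or timing of pre-remission events among responders, the output is unbiased at best and otherwise too high, by nothing up to about threefold. The direction is certain; the size rests on the assumed rates, timing and CR splits above. The median is the most exposed output in a CR-only group of about 17.

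The wording gap in the nine rules rests on no assumption. Twelve counts definitions: running RBC and platelets separately gives 6 + 9 = 15 analyses per treatment group, and the optional serious haemorrhage and infection versions add 6 more, making 21.

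Neither a large overstatement nor an exaggerated benefit of remission is shown. The change is worth making because the outputs invite misreading and the correction is simple.

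**What to change.** 1. For the twelve definitions, make the main summary n/N of responders with at least one event from first dose to first remission, with a Clopper-Pearson 95% CI, which the SAP already uses for response rates. Cumulative incidence with remission as a competing event is an equivalent choice when the time course is wanted.
2. Add events per patient-month before remission and the same rate after it.
3. If Kaplan-Meier is kept, label it as event risk while not yet in remission, and do not present its median as the time by which half of responders had an event.
4. In the nine censoring sentences of 8.1.9.2 to 8.1.9.4, add the restriction that 8.1.9.1 already has: *before achieving CR* (or *CRh*, *CR/CRh*).

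The cost is SAP wording and simpler tables. No new data are needed.
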